8.2 SAFETY AND OTHER ASSESSMENTS

Several procedures and evaluations in SARA-INT clinical protocol will be performed to monitor the study intervention's safety. Some of those are necessary for other purposes (e.g., screening, eligibility, and enrollment).

• **Physical examination:** a standard medical exam of all organ systems to detect possible concomitant conditions that could represent an exclusion criterion (e.g. food ulcer, lower limbs arterial insufficiency, severe respiratory condition, etc.)

- **Anthropometry**: includes height and weight, subcutaneous tissue thickness (with the help of a plicometer) and various circumference measurements
- Short Form -Mini Nutritional Assessment (SF-MNA): this is a 6-question short form of the MNA that can be completed in 5 minutes or less. The MNA has been validated in international studies with a broad range of HCPs in a variety of settings. Currently, this instrument is administered by healthcare professionals to determine patients' nutritional status (Huhmann et al, 2013)⁶¹
- Vital signs (pulse and blood pressure) are measured at screening, M1, M3 and M6 (or endof-study) visits. These are measured twice, in lying or sitting and standing positions
- Electrocardiograms (ECGs): this is performed for screening purposes only. It will be read locally, in order to exclude any underlying cardiac diseases that could represent an exclusion criteria. Meaningful abnormalities will be reported on the eCRF. The original will be kept in the source documents. This should be conducted prior to the start of any physical functional assessments (e.g. the 400MW test) for the safety of the study participants
- Radiographic or other imaging assessments: 1) DEXA scan in SARA-INT is mostly devoted to assess body composition in terms of appendicular lean body mass, at screening visit and M6 (or end-of-study visit). DEXA scans could be performed up to 8 weeks before randomization and enrollment. 2) Gallbladder ultrasound: this is required during screening to exclude previous or active hepatobiliary diseases (e.g. cholestasis/biliary tract obstruction, cholelithiasis, cholecystitis, etc.), and is repeated at the end of the treatment (M6 visit) to assess any emergent hepatobiliary abnormalities
- **Biological specimen collection and laboratory evaluations:** Blood samples will be collected by venepuncture or via indwelling cannula at screening, M1, M3 and at M6 visits for biochemistry and analyses. In case of previous abnormalities or new symptoms, a blood sample can be collected at M5
 - a. **Hematology**: hemoglobin, HbA1c, hematocrit, red blood cell (RBC) count, white blood cell (WBC) count with differential, platelet count, mean corpuscular haemoglobin, mean corpuscular haemoglobin concentration, mean corpuscular volume
 - b. Biochemistry: sodium, potassium, chloride, bicarbonate, urea, uric acid creatinine, albumin, glucose, cholesterol (total cholesterol, LDL, HDL fractions), triglycerides, aspartate aminotransferase (AST), alanine aminotransferase (ALT), alkaline phosphatase, bone-specific alkaline phosphatase, lipase, amylase, gamma glutamyl aminotransferase, bilirubin (total, indirect, direct), creatine phosphokinase and mb-creatine phosphokinase, lactate dehydrogenase, total protein, and GFR estimation based on Cockroft & Gault calculation
 - c. **Coagulation**: activated partial thromboplastin time, prothrombin time, and international normalized ratio.
 - d. **Urine analysis**: A midstream urine sample will be collected for urinalysis by dipstick for glucose, protein, and occult blood

All study analyses will be performed by a centralized laboratory. The Investigator must review the laboratory report, document this review, and record any changes occurred during the study. Laboratory values outside the normal ranges will be flagged and their clinical relevance will be assessed by the Investigator. **See also Exclusion criteria based on lab results and stopping rules in Section 5.3** Exclusion criteria and temporary exclusion criteria and **Section 7.1** discontinuation of study intervention, respectively.

- **Counseling procedures, including any dietary or activity considerations**: see section 5.4 Lifestyle considerations
- Assessment of study intervention adherence: see Study Intervention Compliance, section 6.4
- Administration of the PROs: see Efficacy Assessments, Section 8.1
- Assessment of AEs: At each visit, participants will be explicitly asked to report any new symptoms or any newly observed abnormality since the previous study visit. An unsolicited AE is one reported without any prompting or in response to a general question such as "Have you noticed anything different since you started the study, since you began the study intervention and etc.". A solicited AE is one that is specifically solicited such as "Have you noticed any falls since you started the study medication?". Ongoing AEs/SAEs will be followed up until resolution or clinical stabilization. See also Section 8.3.4, Time Period and Frequency for Event Assessment and Follow-Up.

Participants will be provided with the results of their ECG and laboratory analyses.

Due to the COVID-19 situation and safety concerns over viral transmission, every investigational visit within the protocol is now be performed remotely (e.g. by phone) for all participants still active in the study by the investigational site staff. The investigational site will continue to monitor the health status of the participants by collecting information on general health status, Concomitant Medication and Adverse Events.

M7.5 and M10.5 phone calls include a pre-diabetic questionnaire as recommended by

8.3 ADVERSE EVENTS AND SERIOUS ADVERSE EVENTS

8.3.1 DEFINITION OF ADVERSE EVENTS (AE)

An adverse event means any untoward medical occurrence associated with the use of an intervention in humans, whether or not considered intervention-related (21 CFR 312.32 (a)).

8.3.2 DEFINITION OF SERIOUS ADVERSE EVENTS (SAE)

An AE is considered "serious" if, in the view of either the investigator or sponsor, it results in any of the following outcomes: death, a life-threatening AE, inpatient hospitalization or prolongation of existing hospitalization, a persistent or significant incapacity or substantial disruption of the ability to conduct normal life functions, or a congenital anomaly/birth defect. Important medical events that may not result in death, be life-threatening, or require hospitalization may be considered serious when, based upon appropriate medical judgment, they may jeopardize the patient or subject and may require medical or surgical intervention to prevent one of the outcomes listed in this definition. Examples of such medical events include allergic bronchospasm requiring intensive treatment in an emergency room or at home, blood dyscrasias or convulsions that do not result in inpatient hospitalization, or the development of drug dependency or drug abuse.

8.3.3 CLASSIFICATION OF AN ADVERSE EVENT

8.3.3.1 SEVERITY OF EVENT

For AEs not included in the protocol-defined grading system, the following guidelines will be used to describe severity:

- **Mild** Events that require minimal or no treatment and do not interfere with the study participant's daily activities
- **Moderate** Events that result in a low level of inconvenience or concern with the therapeutic measures. Moderate events may cause some interference with functioning
- Severe Events that interrupt a participant's usual daily activity and may require systemic drug therapy or other treatment. Severe events are usually potentially life-threatening or incapacitating. Of note, the term "severe" does not necessarily equate to "serious"

8.3.3.2 RELATIONSHIP TO STUDY INTERVENTION

All AEs must have their relationship to the study intervention assessed by the clinician who examines and evaluates the study participant based on the temporal relationship between the occurrence of the AE and the study drug administration and based on his/her clinical judgment. The degree of certainty about any causality will be graded using the categories below. In a clinical trial, the study product must always be suspected.

- **Definitely Related** There is clear evidence to suggest a causal relationship, and other possible contributing factors can be ruled out. The clinical event, including an abnormal laboratory test result, occurs in a plausible time relationship to study intervention administration and cannot be explained by concurrent disease or other drugs or chemicals. The response to withdrawal of the study intervention (de-challenge) should be clinically plausible. The event must be pharmacologically or phenomenologically definitive, with use of a satisfactory re-challenge procedure if necessary.
- **Probably Related** There is evidence to suggest a causal relationship, and the influence of other factors is unlikely. The clinical event, including an abnormal laboratory test result, occurs within a reasonable time after administration of the study intervention, is unlikely to be attributed to concurrent disease or other drugs or chemicals, and follows a clinically reasonable response on withdrawal (de-challenge). Re-challenge information is not required to fulfill this definition.
- Potentially Related There is some evidence to suggest a causal relationship (e.g., the event occurred within a reasonable time after administration of the trial medication). However, other factors may have contributed to the event (e.g., the participant's clinical condition, other concomitant events). Although an AE may rate only as "potentially related" soon after discovery, it can be flagged as requiring more information and later be upgraded to "probably related" or "definitely related", as appropriate.
- Unlikely to be related A clinical event, including an abnormal laboratory test result, whose temporal relationship to study intervention administration makes a causal relationship improbable (e.g., the event did not occur within a reasonable time after administration of the study intervention) and in which other drugs or chemicals or underlying disease provides plausible explanations (e.g., the participant's clinical condition, other concomitant treatments).
- Not Related The AE is completely independent of study intervention administration, and/or evidence exists that the event is definitely related to another etiology. There must be an alternative, definitive etiology documented by the clinician.

For any reported AE, the study investigator will report the relationship to study intervention in the eCRF.

8.3.3.3 EXPECTEDNESS

The DSMB will be responsible for determining whether an AE is expected or unexpected. An AE will be considered unexpected if the nature, severity, or frequency of the event is not consistent with the risk information previously described for the study intervention.

The expectedness determination will take place during periodic reviews, or exceptional reviews, as needed.

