8.3.6 SERIOUS ADVERSE EVENT REPORTING

The study clinician will immediately report to the sponsor of any SAEs, whether or not considered study intervention related, including those listed in the protocol or investigator brochure, and must include an assessment of whether there is a reasonable possibility that the study intervention caused the event. Study endpoints that are SAEs (e.g. all-cause mortality) must be reported in accordance with the protocol unless there is evidence suggesting a causal relationship between the study intervention and the event (e.g. death from anaphylaxis). In that case, the investigator must immediately report the event to the sponsor.

All SAEs will be followed until satisfactory resolution or until the site investigator deems the event to be chronic or the participant is stable. Other supporting documentation of the event may be requested by the Data Coordinating Center (DCC)/study sponsor and should be provided as soon as possible.

The study sponsor will be responsible for notifying the FDA of any unexpected fatal or lifethreatening suspected adverse reaction as soon as possible, but in no case later than 7 calendar days after the sponsor's initial receipt of the information. In addition, the sponsor must notify the FDA and all participating investigators in an Investigational New Drug (IND) safety report of potential serious risks, from clinical trials or any other source, as soon as possible, but in no case later than 15 calendar days after the sponsor determines that the information qualifies for reporting.

Follow-up information on SAEs must also be reported by the investigator within the same time frames.

If a non-serious AE becomes serious, this and other relevant follow-up information must also be provided to within one day as described above. For a non-serious AE that becomes serious but which is not fatal or life-threatening, a complete clinical report should be received within 5 days.

The following variables will be recorded for each AE: verbatim AE description, time and date for AE start and stop, maximum intensity, seriousness, causality rating, whether or not the AE caused the patient to discontinue, and the outcome.

All SAEs have to be reported, whether or not considered causally related to the study procedures. All SAEs will be recorded in the eCRF. The investigator is responsible for informing the IEC/IRB of the SAE based on local requirements.

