8.4.2 UNANTICIPATED PROBLEM REPORTING

The investigator will report all medically relevant UPs to **principal investigator (PI)**, Sponsor, the DSMB and the reviewing IRB. The UP report will include the following information:

- Protocol identification information including protocol title and number, Pl's name, and the IRB project number
- A detailed description of the event, incident, experience, or outcome
- An explanation of the basis for determining that the event, incident, experience, or outcome represents an UP
- A description of any changes to the protocol or other corrective actions that have been taken or are proposed in response to the UP

To satisfy the requirement for prompt reporting, UPs will be reported using the following timeline:

- UPs that are SAEs will be reported to the IRB and to the DCC/study sponsor within 24 h of the investigator becoming aware of the event
- Any other UPs will be reported to the IRB and to the study sponsor within 7 days of the investigator becoming aware of the problem

 All UPs should be reported to appropriate institutional officials (as required by an institution's written reporting procedures), the supporting agency head (or designee), and the OHRP within 15 days of the IRB's receipt of the report of the problem from the investigator

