The Biophytis Chief Medical Officer will act as Secretary of the Steering Committee. The Steering Committee will be able to invite other experts from Biophytis and Biophytis subcontractors, e.g.

clinical operations, clinical development, etc. as deemed necessary for the purpose of the meetings.

The Plenum

The Plenum consists of all SARA-INT Investigators and will be chaired by the Coordinator. The Plenum can be asked to meet and advise on topics and issues related to the good implementation of the clinical operations, their possible improvements and/or opportune changes.

The Plenum will meet at least once a year to conduct a general project review and project outlook and will meet via teleconference in case an urgent decision has to be undertaken based on their advice.

The Data Safety Monitoring Board (DSMB)

The DSMB is periodically reviewing all safety data and raise alerts in case of negative or dangerous findings. Members of the DSMB will be selected based on their expertise by the SARA managing Board.

During the COVID-19 outbreak, the DSMB is meeting at least every other week to review its recommendation based on update of guidance from the national health agencies and local status.

The Adjudication Committee

The committee will specifically adjudicate the primary end -point, i.e. the 400MW test, in those cases where patients either did not show up or were not able to be tested after 6 months of treatment. Adjudication will be based on the medical dossier and, when available, on the results to a proxy of the 400MW test, e.g. the walking speed of the 4-meter test of SPPB, (for rules of conversion see MCDermott, 2007⁵⁸) with a comprehensive individual case objective evaluation. Precise rules will be endorsed by the adjudication committee at the first meeting and will then made available in the study handbook and its digital version on SARA portal.

Any effort will be undertaken to contact and evaluate patients temporarily lost to follow-up, including home visits where feasible.

The Scientific Advisory Board (SAB)

This is an independent advisory committee, able to advise and discuss the overall study conduct and scientific basis in view of ongoing progress of knowledge within the scientific community. The SAB will meet yearly and may ask DSMB questions and recommend specific actions to the other governance committees.

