10.1.6 SAFETY OVERSIGHT

Safety oversight will be under the direction of a DSMB composed of individuals with the appropriate expertise, including geriatrics, gerontology, clinical trial methodology, human and clinical nutrition, internal medicine, bioethics, data privacy and ethics of information technologies, information and communication technologies applied to health (e-health). Members of the DSMB should be independent from the study conduct and free of conflict of interest, or measures should be in place to minimize perceived conflict of interest. The DSMB will meet quarterly to assess safety data of all study participants enrolled in the study. The DMSB will operate under the rules of an approved charter that will be written and reviewed at the organizational meeting of the DSMB. At this time, each data element that the DSMB needs to assess will be clearly defined. The DSMB will provide its input to the Study Managing Board and will answer questions from the Steering Committee and the Scientific Advisory Board.

the DSMB will review

bioanalytical data and other relevant safety data each 3 calendar months once the 25th patient is randomized and starts the investigational drug administration. The DSMB can trigger interim PK analysis of collected blood samples by a third party in order to avoid the unblinding of the study.

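### Expectedness is left to DSMB reviews with no stated trigger or turnaround, while the 7-day FDA notice that depends on it runs from the sponsor's first receipt

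*Protocol*

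**What the plan says.** Protocol 8.3.3.3 (Expectedness): "The DSMB will be responsible for determining whether an AE is expected or unexpected". On timing: "The expectedness determination will take place during periodic reviews, or exceptional reviews, as needed". The benchmark is the risk information already described for the study intervention. The section does not say who calls an exceptional review, on what event, or how quickly the board must answer.

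Protocol 10.1.6 (Safety Oversight): "The DSMB will meet quarterly to assess safety data of all study participants enrolled in the study". Section 10.1.5 adds: "During the COVID-19 outbreak, the DSMB is meeting at least every other week to review its recommendation", the stated reason being updated guidance from health agencies and local conditions.

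Protocol 8.3.6 (Serious Adverse Event Reporting): "The study sponsor will be responsible for notifying the FDA of any unexpected fatal or lifethreatening suspected adverse reaction as soon as possible", and "in no case later than 7 calendar days after the sponsor's initial receipt of the information". The same section has every SAE sent to the sponsor immediately, whatever its relationship to treatment, and has the investigator inform the ethics committee or IRB under local requirements.

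Protocol 8.4.1 makes being unexpected one of the criteria for an unanticipated problem (UP), using the OHRP definition. Under 8.4.2 the investigator reports UPs to the principal investigator, the sponsor, the DSMB and the IRB, and must explain why the event counts as one. On timing: "UPs that are SAEs will be reported to the IRB and to the DCC/study sponsor within 24 h" of the investigator becoming aware; other UPs have 7 days.

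**The concern.** An expedited report needs three judgements: seriousness, causality and expectedness. The protocol gives seriousness to the investigator or sponsor (8.3.2) and the causality assessment to the examining clinician (8.3.3.2, 8.3.6), all of whom are close to the case. Only expectedness goes to a board that works through meetings. Yet the 7-day FDA notice turns on that third judgement, and its clock starts when the sponsor first hears of the event. The party that must file on time does not hold the decision that makes the event reportable.

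The 7-day notice covers the gravest category, unexpected fatal or life-threatening suspected reactions. It arises here in older adults with chronic disease whose exposure may run to 39 weeks. Followed literally, 8.3.3.3 would have the sponsor wait for a review while the limit expires.

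The UP sections raise a related difficulty. They put a judgement about unexpectedness in the investigator's hands, without saying how it relates to the determination that 8.3.3.3 gives to the DSMB.

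**Working it through.** The documents give no figure for the time to an expectedness decision, so there is none to reproduce. The check compares the length of each clock with the interval between scheduled reviews.

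**Inputs**
- Routine interval: quarterly (10.1.6), T = 365.25 / 4 = 91.3 days.
- Outbreak interval: at least every other week (10.1.5), so T = 14 days at most.
- FDA notice: c = 7 days from the sponsor's initial receipt (8.3.6).
- UP reports: c = 1 day (SAEs) or 7 days (others) from the investigator's awareness (8.4.2).

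**Assumption.** Cases arrive evenly between scheduled reviews. The documents give no arrival pattern.

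**Formulas**
- Chance that the next scheduled review falls inside the clock = min(1, c / T)
- Mean wait = T / 2
- Longest overrun = T − c

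**Results for the 7-day FDA clock**

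| Schedule | Within 7 days | Mean wait | Longest overrun |
|---|---|---|---|
| Quarterly | 7 / 91.3 = 7.7% | 91.3 / 2 = 45.7 days | 91.3 − 7 = 84.3 days |
| Every other week | 7 / 14 = 50% | 14 / 2 = 7 days | 14 − 7 = 7 days |

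Neither schedule guarantees a review in time. These figures describe scheduled reviews only. They do not estimate how often a report would be late, because 8.3.3.3 also allows exceptional reviews.

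**UP clocks.** If a scheduled DSMB decision were needed first, the 24-hour limit would be met in 1 / 91.3 = 1.1% of cases (quarterly) or 1 / 14 = 7.1% (fortnightly). Whether it is needed depends on which section governs:
- If 8.3.3.3 governs, the process is circular. The board must class the event as unexpected before the investigator can send the report that, under 8.4.2, notifies the board.
- If 8.4 governs, the investigator decides under the OHRP definition, whose benchmark is the protocol-related documents and the population studied. No DSMB wait arises, but 8.3.3.3 then claims more for the DSMB than it has.

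The second reading fits 8.4.2 better, since the investigator must justify the classification. On that reading the fault is two decision-makers left unreconciled, and the 1.1% and 7.1% do not apply.

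**The case against.** The strongest defence is that 8.3.3.3 does not confine the board to its calendar. An exceptional review could be held within 7 days, 8.3.6 sets a hard limit that 8.3.3.3 does not relax, and the UP report gives the board a route to hear of a case. The DSMB charter, which is not available here, may set a turnaround, and parts of the governance and safety text are blanked or removed. This stands to the extent that the plan as a whole cannot be said to lack a trigger; only the available protocol text can. It does not remove the gap, because the text that sites and sponsor follow makes a timed duty depend on an untimed decision.

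It can also be said that one sentence setting a turnaround for exceptional reviews would be enough. That would close the gap, but it would convene a board for a case-level comparison that the sponsor, who already receives every SAE and must file, can make directly.

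A reader might infer more than the documents support:
- **That the 15-day reports would also be late.** The IND safety report runs from the sponsor's own determination that the information qualifies, and the OHRP report from the IRB's receipt of the investigator's report. A DSMB wait could postpone those starts but would not breach either limit as written.
- **That IRBs would learn of SAEs weeks late.** SAEs go to the sponsor at once and to ethics committees under local requirements, with no expectedness condition.
- **That the arrangement threatens the blind.** SAP 3.2 says the DSMB is unblinded for its reviews, but comparing an event with known risk information needs no allocation, and nothing describes allocation returning to blinded staff.

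**Conclusion.** The point holds for the 7-day FDA notice. It depends on an expectedness decision that 8.3.3.3 gives to the DSMB without a trigger or turnaround, and its clock runs from the sponsor's first receipt. Scheduled reviews would fall inside the clock for about 8% of cases under quarterly meetings and 50% under fortnightly ones, assuming even arrival. The 50% also assumes that the outbreak meetings would take up expectedness, which is not their stated purpose. Timely filing therefore rests wholly on exceptional reviews that the available text does not define.

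For UPs the finding is narrower: 8.3.3.3 and 8.4 name different decision-makers and benchmarks for whether an event is unexpected, and do not say which applies.

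The change should be made, but the exposure is limited. First-line SAE reporting is intact, and a sponsor could work around the wording in practice.

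**What to change.** Reword 8.3.3.3, and align 8.3.6, 8.4 and 10.1.6 with it:
1. For expedited reporting, the blinded safety function of the sponsor or safety CRO determines expectedness case by case on receipt, against the existing risk information for the study intervention, in time for the 7-day limit in 8.3.6.
2. For UP reports under 8.4, the investigator makes the judgement that an event is unexpected, within the 24-hour and 7-day limits already stated.
3. The DSMB receives these cases and reviews them in aggregate at its meetings.

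The cost is protocol wording and a matching line in the DSMB charter. The sponsor already receives every SAE and carries the notification duty, so no extra data collection or board meeting is needed.
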